9.1.5. Adverse Events Leading to FAI Insert Removal

A summary of TEAEs with an action taken with study treatment of "FAI Insert Removal" will be presented in a table by treatment group and all treated eyes. These TEAEs will be also summarized for subject level.

The summary of TEAEs with an action taken with study treatment of "FAI Insert Removal" will be presented by SOC and PT in a manner similar to that described in Section 9.1.1.

9.1.6. Adverse Events Leading to Study Discontinuation

All eyes having an AE where the answer to "Was eye terminated from study due to this AE?" is "Yes" will be presented in a listing.

9.1.7. Adverse Events Leading to Death

All subjects who have an AE with an outcome of "Fatal" will be presented in a listing.

9.1.8. Adverse Events of Special Interest

A summary of TEAEs of cataract and elevated IOP will be presented in a table by treatment group and all treated eyes. These TEAEs will be also summarized for subject level. Events will be included in the summary based on a list of PTs for each event category. Cataract events will include any event whose MedDRA higher lever coded term is "CATARACT CONDITIONS" is contained in the preferred term. IOP elevations will be based on the specific preferred term "INTRAOCULAR PRESSURE INCREASED" or if the preferred term contains the phrase "GLAUCOMA".

A summary of ocular TEAEs which are considered complications of IOP lowering medications to control IOP will be presented by treatment group and all treated eyes. These TEAEs will be also summarized for subject level. Events will be included in the summary based on manual review of AEs with an onset date on or after the date of first use of any IOP lowering medication.

A summary of ocular TEAEs which are considered complications of surgical interventions to control IOP will be presented by treatment group and all treated eyes. These TEAEs will be also summarized for subject level. Events will be included in the summary based on manual review of all AEs with an onset date on or after the date of surgical intervention. A similar summary will be presented for complications of cataract surgeries.

At each level of eye summarization, an eye is counted once for multiple events within PT. Percentages will be calculated out of the number of eyes in the Safety population. At each level of subject summarization, a subject is counted once for multiple events within PT. Percentages will be calculated out of the number of subjects in the Safety population. The summary will be sorted by PT in alphabetical order. Adverse events of special interest will be summarized at Day 7 and Month 12.

A manual data review memo will be written at the time the manual data reviews are performed. Because investigators may report similar events differently, the memo will be written a the time of the manual review to document the specific details on the preferred terms and other text specifications that are used to identify IOP lowering medications, IOP surgeries, and Cataract surgeries.

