5.2.3. Current benefit-risk profile of the FAI insert

Because the efficacy and safety of the FAI insert in uveitis subjects have not yet been fully evaluated, the current benefit-risk profile is based primarily upon previous human experience with Retisert and Iluvien, as well as the (masked) experience to date in PSV-FAI-001. Currently, all data are consistent with the expected benefit-risk profile of the FAI insert; subjects are expected to experience a significant decrease in the frequency of recurrence of uveitis, and are expected to most frequently experience an adverse event associated with cataract or elevated IOP.

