8.2. Subject Exclusion Criteria

- 1. Allergy to fluocinolone acetonide or any component of the FAI insert
- 2. Ocular malignancy in either eye, including choroidal melanoma
- 3. Uveitis with infectious etiology
- 4. Current viral diseases of the cornea and conjunctiva including epithelial herpes simplex keratitis (dendritic keratitis), vaccinia, and varicella
- 5. Current mycobacterial infections of the eye or fungal diseases of ocular structures
- 6. Subjects who yield, during screening, a confirmed positive test for human immune deficiency virus (HIV) or syphilis
- 7. Systemic infection within 30 days prior to study Day 1
- 8. Peripheral retinal detachment in area of insertion
- 9. Elevated intraocular pressure (IOP) > 21 mmHg, or chronic hypotony < 6 mmHg
- 10. Concurrent therapy at Screening with IOP-lowering pharmacologic agent in the study eye
- 11. Current diagnosis of any form of glaucoma or ocular hypertension in study eye at Screening, unless study eye has been previously treated with an incisional surgery procedure that has resulted in stable IOP in the normal range (10-21 mmHg)
- 12. Known history of clinically significant IOP elevation in response to steroid treatment in either eye, unless study eye has been previously treated with an incisional surgery procedure that has resulted in stable IOP in the normal range (10-21 mmHg)
- 13. Ocular surgery or capsulotomy performed on the study eye within 30 days prior to study Day 1
- 14. Intravitreal treatment of study eye: with FAI insert within 36 months prior to study Day 1; with Retisert within 30 months prior to study Day 1; with Ozurdex within 90 days prior to study Day 1; or with Triesence or Trivaris within 30 days prior to study Day 1
- 15. Peri-ocular or subtenon steroid treatment of study eye within 30 days prior to study Day 1
- 16. Treatment with an investigational drug or device within 30 days prior to study Day 1, except the FAI insert within this protocol

- 17. Pregnant or nursing females; females of childbearing potential who are unwilling or unable to use an acceptable method of contraception as outlined in this protocol from at least 14 days prior to study Day 1 until the Month 12 Visit
- 18. Any condition which, in the judgment of the Investigator, could make the subject inappropriate for entry into this study

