11.3. Recording of Adverse Events

Medical conditions or diseases present before a subject starts study treatment are only considered AEs if they worsen after the start of the study treatment.

Adverse events can be spontaneously reported or elicited at each study visit through open-ended questioning, examination or evaluation of a subject. In order to prevent reporting bias, subjects should not be questioned regarding the specific occurrence of one or more AEs.

The Investigator will record all AEs of enrolled subjects in the appropriate eCRF. If known, the diagnosis of the underlying illness or disorder should be recorded, rather than its individual symptoms.

The following information should be captured for all AEs: onset and end date, severity, seriousness, relationship to investigational product, action taken, treatment required and outcome. If treatment for the AE was administered, it should be recorded on the appropriate eCRF page.

Completion of supplemental eCRF pages may be requested for AEs and/or laboratory abnormalities that are reported / identified during the course of the study.

The Investigator will take or organize all appropriate and necessary therapeutic measures required for resolution of the adverse event. Any medication necessary for the treatment of an adverse event must be recorded on the concomitant medication eCRF. If more than one distinct AE occurs, each event should be recorded separately.

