3.1. Overall Study Design and Plan

This trial is a 12 month, phase 3, multi-center, randomized, single-masked (subject), controlled study designed to evaluate the utilization and safety of the Mk II inserter and the safety of the FAI insert, in subjects with non-infectious uveitis affecting the posterior segment of the eye. This study will be conducted in at least 3 study sites. Enrollment of approximately 25 subjects is expected. A total enrollment of approximately 30 eyes is planned for this study (20 Mk II inserter: 10 Mk I inserter) in one or both eyes in each subject.

All subjects will receive the FAI insert on Day 1 of the study, administered using either an Mk I inserter or an Mk II inserter. If both eyes in a subject with bilateral uveitis satisfy the study's inclusion/exclusion criteria, both eyes may be enrolled in the study. In this case, randomization of a subject's second eye will occur independently and will occur no earlier than the study Day 7 visit for the subject's first study eye.

At least 10 different investigators will administer the FAI insert. Each time a subject's eye is enrolled in the study, one investigator will serve as the treating investigator (Investigator); another staff member in the study site will serve as the trained observer (Observer). On study Day 1, the Investigator will administer the FAI insert, and the Observer will observe the procedure used by the Investigator to administer the FAI insert. The Investigator and the Observer will complete questionnaires related to the administration of the FAI insert on Day 1. The Investigator (or designee) will perform all subsequent study assessments. Study personnel will not disclose to the subject which inserter was used for intravitreal administration of the FAI insert.

Subjects will receive standard care in the study eye(s) and any non-study eye for 12 months following enrollment, in accord with medical need and the Investigator's standard practice. Eyes will be assessed according to the schedule of procedures and assessments (Appendix 13.1).

Analyses of study data will be performed at the following two time points during the study:

- 1. After all subjects have completed the Day 7 visit (or have been discontinued from the study prior to this visit). The primary utilization and safety analyses of the inserters will be conducted at Day 7 time point.

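### The elevated-IOP special-interest rule in SAP 9.1.8 would leave out an event coded as ocular hypertension, so that one table may under-count and disagree with the other IOP summaries

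*SAP*

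**What the plan says.** SAP 9.1.8 plans a summary of treatment-emergent cataract and elevated-IOP events, by treatment group and for all treated eyes, at Day 7 and Month 12. Entry is by term: "Events will be included in the summary based on a list of PTs for each event category". For pressure, "IOP elevations will be based on the specific preferred term" INTRAOCULAR PRESSURE INCREASED, "or if the preferred term contains the phrase" GLAUCOMA. The cataract category works differently, since it draws on a higher-level MedDRA term.

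The same section describes manual reviews, but they look for complications of IOP-lowering medication, of IOP surgery and of cataract surgery. The review memo is to record the terms and text "that are used to identify IOP lowering medications, IOP surgeries, and Cataract surgeries". Elevated-IOP adverse events are not on that list.

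Three places in the protocol bear on the rule:
- Section 8.2, criterion 11, excludes a "Current diagnosis of any form of glaucoma or ocular hypertension in study eye at Screening", subject to an exception for earlier incisional surgery. Glaucoma and ocular hypertension are thus named as two conditions.
- Section 11.3 says that, where it is known, "the diagnosis of the underlying illness or disorder should be recorded, rather than its individual symptoms".
- Section 5.2.3 says that subjects "are expected to most frequently experience an adverse event associated with cataract or elevated IOP".

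**The concern.** A table meant to count raised-pressure events should not depend on which of two near-equivalent labels the investigator chose. The rule takes in every form of glaucoma and one exact term for raised pressure, but it passes over the other diagnosis that the protocol sets beside glaucoma. If an event is reported and coded as ocular hypertension, the eye is missing from the elevated-IOP category unless it has another qualifying event.

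Two things are at stake. The first is the completeness of a table on one of the two kinds of event that the sponsor expects most often. The second is consistency: the same eye could appear as raised pressure in the measured-IOP or medication tables and be absent from the special-interest table. The groups are small enough for one eye to be visible in the percentages.

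**Working it through.** The plan gives no figure for this table, so there is none to reproduce. The check is a literal application of the rule, a search for anything that would repair it, and the arithmetic of one missed eye.

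**Step 1. The rule as a test (SAP 9.1.8).** Include an event if its preferred term equals INTRAOCULAR PRESSURE INCREASED, or if the term contains GLAUCOMA.

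| Preferred term | Equals first term | Contains GLAUCOMA | In table |
|---|---|---|---|
| INTRAOCULAR PRESSURE INCREASED | yes | no | yes |
| GLAUCOMA | no | yes | yes |
| NEOVASCULAR GLAUCOMA | no | yes | yes |
| OCULAR HYPERTENSION | no | no | **no** |

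**Step 2. Does another provision add the event to this table?** The manual reviews and the memo in SAP 9.1.8 deal with treatments and their complications, not with this category. SAP 7.2.1 has a safeguard for IOP surgery, where records with an unspecific reason are checked against their free text. No equivalent is stated for elevated-IOP adverse events. SAP 9.1.8 itself acknowledges that investigators may word similar events in different ways, but it applies that remark to the medication and surgery searches.

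**Step 3. Where would the event still appear?**
- SAP 9.1.1, ocular events by system organ class and preferred term: always, on its own row.
- SAP 9.1.1, protocol-defined ocular events: if the rise is at least 10 mmHg at two visits at least a week apart, or IOP reaches 25 mmHg or more.
- SAP 9.2.2, measured IOP: if a recorded value exceeds 21, 25 or 30 mmHg, or rises from baseline by more than 5 or by at least 12 mmHg.
- SAP 7.1.3, IOP-lowering medication (Month 12 only): if the medication is recorded with increased IOP as the reason and meets the minimum duration.

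**Step 4. Size per eye.** The denominators come from SAP 3.1: "A total enrollment of approximately 30 eyes is planned for this study (20 Mk II inserter: 10 Mk I inserter". For k eyes whose only IOP event is coded as ocular hypertension, all in the group shown, the rate is low by 100 × k / n percentage points.

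| Group | n | k = 1 | k = 2 |
|---|---|---|---|
| Mk I | 10 | 100 × 1/10 = 10.0 | 100 × 2/10 = 20.0 |
| Mk II | 20 | 100 × 1/20 = 5.0 | 100 × 2/20 = 10.0 |
| All eyes | 30 | 100 × 1/30 = 3.3 | 100 × 2/30 = 6.7 |

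The documents do not give k. The range of 0 to 2 is an assumption for illustration, and at k = 0 nothing changes. An eye that also has a qualifying event stays in the elevated-IOP category and does not count towards k.

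**The case against.** The strongest reply is that raised pressure is well covered without this table. Measured values, protocol-defined events, IOP-lowering medication and IOP surgery are all tabulated by routes that do not depend on the preferred term, and an ocular hypertension term would have its own row in the general adverse event table. This stands, and it limits the point. A reader might infer that the 12-month safety conclusion as a whole would understate raised pressure. The documents do not support that, because the event is missing from one descriptive table and visible in at least one other. The other routes still do not do this table's job. The general table leaves the reader to combine rows without counting an eye twice, and the remaining summaries need thresholds, durations or reasons to be met.

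A second reply is that such a report may be rare. The protocol's own wording for these events is elevated or increased IOP, and the serious events listed in Protocol 5.2.2.3 include elevated IOP and neovascular glaucoma but not ocular hypertension. This also stands, although that list is short and covers serious events only. A reader might want to assume a share of events reported as ocular hypertension and turn it into a percentage under-count, but nothing in the documents supports a share. Nor does Protocol 11.3 oblige anyone to relabel a pressure reading: it speaks of symptoms, and of a diagnosis where one is known. It makes a diagnostic term plausible, no more.

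Third, the coding dictionary is not in the documents. If a coder maps the report to INTRAOCULAR PRESSURE INCREASED, nothing is lost.

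Finally, the SAP counts each eye once per preferred term and does not expressly promise a pooled elevated-IOP row. If only term rows are shown, the effect is a missing row rather than a low total.

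**Conclusion.** The gap is real and narrow. Read literally, the rule omits a condition that the protocol names beside glaucoma, and no stated review puts it back. The consequence is a possible under-count in the special-interest table at Day 7 and Month 12, and possible disagreement with the IOP summaries in SAP 7.1.3, 9.1.1 and 9.2.2.

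The per-eye sizes in the working rest on three assumptions: the event keeps its own preferred term, the eye has no other qualifying event, and the planned group sizes are reached. The number of such eyes is unknown and may be zero. The primary utilization result is not affected. The change is worth making because it costs almost nothing and makes the table complete for the event it is meant to count.

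**What to change.** Before the Day 7 database lock, amend the elevated-IOP list in SAP 9.1.8 so that it also takes any preferred term containing OCULAR HYPERTENSION, and change the table program to match. The cost is one string in the SAP and one in the program. The reported incidence may rise slightly.

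Optionally, extend the manual data review memo to the elevated-IOP category: someone masked to inserter reads the list of ocular preferred terms, confirms that no other raised-pressure term has been missed, and records the decision. The memo does not now cover this table, so this would be a new task, though a short one in a study of about 30 eyes.

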Continuous data will be described using descriptive statistics (i.e. n, mean, standard deviation, median, minimum, and maximum). Categorical data will be described using the eye/subject count and percentage in each category. For the summary statistics of all numerical variables unless otherwise specified, minimum and maximum will be displayed to the same level of precision as reported. Mean and median will be displayed to one level of precision greater than the data collected. Standard deviation / standard error will be displayed to two levels of precision greater than the data collected. P-values will be rounded to three decimal places. If a p-value is less than 0.001 it will be reported as "<0.001". If a p-value is greater than 0.999 it will be reported as ">0.999".

Data will be displayed in all listings sorted by treatment group, unless otherwise specified. A subject will be assigned by the study site. The first 3 digits of the ID number will be the assigned site number, followed by a 3-digit subject number in sequential order (i.e., 201001, etc.). Within the IWRS system, at the time of randomization, a 1-digit eye identification number will be added: the subject's first eye (if eligible) to be randomized will be assigned the additional digit "1" (e.g., 201001-1); the subject's second eye (if eligible) to be randomized will be assigned the additional digit "2" (e.g., 201001-2). However all data within the clinical data base will be recorded based on the subject number (without the eye id) and eye level data will be recorded as OD or OS. For non-ocular/systemic assessments, subjects who have more than one eye randomized/treated will have data listed once for each different treatment received. (e.g., the data could be listed for both the Mk II and Mk I injectors.)

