If there is more than one observation falling in a defined visit window and one of the observations was made in a "scheduled" study visit (e.g., day 7, day 28, Month 3, etc.) and the other observation(s) was made in an unscheduled visit, then the observation from the scheduled study visit will be used for by-visit analyses.

If there is more than one observation falling into a defined visit window and all observations are from unscheduled visits, then the earliest observation with non-missing data for a given assessment will be used for by-visit analyses.

All assessments will be presented in the data listings.

The Day 7 analysis will include all assessments with a start day on or before the upper limit of the Day 7 visit window (study day 10). The analysis at Month 12 will include all data in the database.

Subjects may have more than one eye randomized to treatment; therefore, for summaries counting patients by treated eye, a subject may be included more than once in a given summary. The same subject may be included more than once in the same treatment group if both eyes are randomized to the same inserter. Similarly, a subject may be counted more than once in the total eyes column if both eyes are randomized.

Subjects will be counted at most once for total subject summaries even if the subject has both eyes randomized.

Eyes not receiving assigned treatment and non-study eyes will have all safety data listed and will be included in selected AE and SAE summaries only. In the listings, randomized eyes that did not receive treatment will be grouped separately by their randomized treatment assignment (i.e., Mk I inserter - Not Treated, Mk II inserter - Not Treated). Non-randomized eyes which do not receive treatment will be grouped in listings. Percentages for Safety population summaries will be based on the number of eyes that received treatment.

All analyses will be conducted using SAS Version 9.2 or higher.

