6.2. Baseline Ocular Characteristics

Baseline ocular characteristics will be summarized by treatment group and for all treated eyes for the ITT and Safety populations. Summaries will be generated for the Safety population only if there are randomized eyes that do not receive treatment.

The baseline ocular characteristics to be summarized include:

- Treated Eyes (OD, OS)
- Duration of uveitis (years) calculated as (screening date date of onset of uveitis +1)/ 365.25
- Number of recurrences in the last 12 months
- Lens status
- Presence of cataract (if with lens status of phakic)
- History of vitrectomy procedure(s)
- Prior incisional anti-glaucoma surgeries
- Baseline BCVA (letters)
- Baseline IOP (mmHg)

Duration of uveitis, baseline BCVA (letters), and baseline IOP (mmHg) will be summarized as continuous variables. For partial uveitis onset dates, a missing month will be imputed as January and a missing day will be imputed as the first of the month. The number and percentage of eyes by duration of uveitis (< 2 years, 2 to 5 years, > 5 years), number or recurrences in the last 12

months (<= 2, >2), lens status (phakic, aphakic, and pseudophakic), presence of cataract (if with lens status of phakic), and history of related procedure(s) and surgeries will also be reported.

Baseline ocular characteristics will be summarized for randomized eyes only. Summaries will be presented at the eye level. Percentage will be based on the number of randomized eyes (ITT) or treated eyes (Safety).

All collected baseline ocular characteristics data for all eyes will be presented in a listing for the ITT population.

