7.2.2 Cataract Surgeries

The number and percentage of eyes requiring cataract surgery will be summarized by treatment group and for all treated eyes. Only eyes which are indicated as phakic at study entry will be included for analysis. Ocular surgeries with a reason of "Cataract" will be included in the summary. Incidence will be summarized overall through 12 months and for 6 month time intervals through 12 months. All summaries will be performed using the Safety population and percentages will be based on the number of phakic eyes in the Safety population. Analysis will be performed for the final analysis at Month 12 only.

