9.2.1. Best-corrected Visual Acuity (BCVA)

BCVA will be measured according to the standard procedure developed for ETDRS at 4 meters (or at 3 meters if the electronic ETDRS system is employed). Corrected-distance VA is to be reported as number of letters read correctly by the subject. The Snellen Fraction will also be recorded. If the subject is unable to read any letters at 4 meters or 1 meter, the investigator will assess the subject's ability to count fingers, recognize hand motion, or light perception.

A summary table presenting the observed values and changes from baseline in BCVA (letters) will be presented by treatment group for the Safety population. Changes from baseline to each scheduled post-baseline visit will be presented. In addition, a categorical summary of change from baseline in BCVA will present the letter change at Day 7 (or Month 12) and the maximum letter change at any time point up to Day 7 (or Month 12), including categories of \geq 15 letters lost, \geq 10 letters lost, \geq 5 letters lost, no change, \geq 5 letters gained, \geq 10 letters gained, and \geq 15 letters gained.

The BCVA summaries will also be presented for the following subgroups:

- IOP lowering medication [No IOP lowering medication, Required IOP lowering medication]
- Surgical Intervention to Control Elevated IOP [No surgical intervention, Required surgical intervention]
- Lens status at Baseline [Phakic, Aphakic, Pseudophakic]

IOP lowering medication status will be based on a subject's use of any IOP lowering medication up to the time point of interest (Day 7 and Month 12). Surgical intervention status will be defined in a similar manner.

For eyes with phakic lens status at study entry who undergo cataract surgery while in the study, the change in BCVA (letters) from the last BCVA measurement prior to surgery to the first BCVA measurement after surgery will be summarized by treatment group for the Safety population. In addition, a summary of change from baseline in BCVA (letters) will be presented by treatment group with phakic eyes at study entry who undergo cataract surgery while in the study vs. eyes with a lens status of pseudophakic at study entry.

BCVA data will be presented in a listing.

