9.2.4. Slit Lamp Examination

The investigator will assess any changes in lens or cataract status and the status (Normal, Abnormal – Clinically Significant, Abnormal – Not Clinically Significant) of the conjunctiva, cornea, iris, anterior chamber, and posterior chamber.

A summary table presenting the number and percentage of eyes with a change in lens/cataract status since screening or a worsening of an existing cataract since the previous visit will be presented by baseline lens status, treatment group for the Safety population with a phakic or pseudophakic lens status at study entry for the given eye.

Data from the slit lamp examination will be presented in a listing.

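### The special-interest cataract percentage is taken over all treated eyes but cataract surgery over phakic eyes, so the cataract figure is diluted if non-phakic eyes enrol

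*SAP*

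**What the plan says.** SAP 9.1.8 tabulates cataract and elevated-IOP TEAEs by treatment group, for all treated eyes and by subject, at Day 7 and Month 12. One rule covers every row. At eye level: "Percentages will be calculated out of the number of eyes in the Safety population". At subject level: "Percentages will be calculated out of the number of subjects in the Safety population". The eye-level rule follows the general convention in SAP section 4: "Percentages for Safety population summaries will be based on the number of eyes that received treatment".

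For cataract surgery, SAP 7.2.2 includes only eyes phakic at study entry, and "percentages will be based on the number of phakic eyes in the Safety population". It reports by arm and for all treated eyes, at Month 12 only.

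Lens status is used elsewhere too. SAP 6.2 tabulates phakic, aphakic and pseudophakic eyes at baseline. SAP 9.2.1 uses lens status as a BCVA subgroup. In SAP 9.2.4 the slit-lamp table of lens or cataract change, including "a worsening of an existing cataract since the previous visit will be presented by baseline lens status", is restricted to eyes phakic or pseudophakic at entry.

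No eligibility criterion restricts lens status. Exclusion 13 in Protocol 8.2 bars ocular surgery on the study eye only within the 30 days before Day 1.

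**The concern.** An eye without its natural lens is not normally at risk of a new or worsening cataract. The SAP recognises this for surgery but not for the event that leads to surgery. Three things follow if non-phakic eyes are treated:

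- The printed cataract percentage is lower than the rate among eyes that could have the event.
- The arms can print different percentages only because their lens mix differs. Randomization is stratified by investigator, not lens status, and the arms are small (about 20 and 10 eyes).
- At Month 12 the cataract and cataract-surgery percentages stand on different bases, so comparing them as printed can mislead.

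Protocol 5.2.3 expects events associated with cataract or elevated IOP to be the most frequent adverse events, and 12-month safety of the insert is the secondary objective. This table is the dedicated summary of that harm.

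**Working it through.** **The plan's own figures.** The only numerical precision statements are the exact binomial intervals in SAP 4.1. Clopper-Pearson gives 27.2-72.8% for 10/20 and 18.7-81.3% for 5/10, as stated. The point does not depend on them, but the same method is used below.

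**Inputs from the documents.** About 30 eyes, 20 Mk II and 10 Mk I, and about 25 subjects (SAP 3.1); denominators as in 9.1.8 and 7.2.2.

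**Assumed inputs.** The documents give no phakic share, event count, number operated or number of bilateral subjects. All are illustrations, with cataract events only in phakic eyes.

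**Eye level.** Let N be treated eyes, P phakic treated eyes and x eyes with a cataract TEAE. Then x/N = (x/P) × (P/N): the printed figure is the at-risk rate times the phakic share. With N = 30 and x = 6:

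| Phakic eyes P | Printed, 6/30 | At-risk, 6/P |
|---|---|---|
| 15 | 20% | 40% |
| 21 | 20% | 29% |
| 27 | 20% | 22% |
| 30 | 20% | 20% |

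**Arms.** Suppose half the phakic eyes in each arm have an event, with 10 of 20 Mk II and 8 of 10 Mk I eyes phakic. The table prints 5/20 = 25% against 4/10 = 40%. On the phakic base both are 50% (5/10 and 4/8).

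How likely is such an imbalance? Assume simple random allocation of 30 eyes 20:10, ignoring the investigator strata, and let X be the number of phakic eyes in the Mk I arm (hypergeometric). The chance that |X/10 − (P − X)/20| is at least 0.20 is about 25% for P = 15, 20% for P = 21 and 3% for P = 27.

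**Cataract against surgery.** With P = 15, 6 eyes with an event and 4 of them operated, the plan prints cataract 6/30 = 20% and surgery 4/15 = 27%. On one base they are 6/15 = 40% and 4/15 = 27%.

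**Subject level.** Take 25 subjects, 20 with one treated eye and 5 with two (20 + 10 = 30 eyes), and the 6 events in 6 different subjects. The table prints 6/25 = 24%. Enumerating how P phakic eyes can fall among these subjects:

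| Phakic eyes P | Subjects with at least one phakic treated eye | At-risk percentage |
|---|---|---|
| 15 | 10 to 15 | 60% to 40% |
| 21 | 16 to 21 | 38% to 29% |
| 27 | 22 to 25 | 27% to 24% |
| 30 | 25 | 24% |

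**Precision on the smaller base.** Exact 95% intervals, treating eyes as independent:

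- 6/30: 7.7-38.6%; 6/15: 16.3-67.7%.
- Mk I arm alone, 2/10: 2.5-55.6%; 2/5: 5.3-85.3%.

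**The case against.** The strongest reply is that nothing here is an error. All treated eyes is the SAP's declared base for safety summaries, 9.1.8 follows it, and it suits the elevated-IOP rows governed by the same sentence. No passage says the 9.1.8 and 7.2.2 percentages are to be compared. This stands: the point is an improvement in presentation, not a contradiction.

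Much of the at-risk information is also already planned. SAP section 4 provides counts: "Categorical data will be described using the eye/subject count and percentage in each category". SAP 7.2.2 gives the phakic denominator by arm. SAP 9.2.4 splits lens and cataract change by baseline lens status, although it rests on slit-lamp findings rather than TEAEs. This also stands, and it limits the harm.

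A reader might infer that the two cataract figures cannot be compared at all, or that the subject-level base is lost because 6.2 is summarised by eye. The documents do not support either reading. At eye level the 9.1.8 count can be set over the 7.2.2 denominator. At subject level the listings of baseline ocular characteristics and of AEs allow a hand count in about 25 subjects. What fails is only the direct reading of the printed percentages.

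Finally, the added rate will be imprecise, as the Mk I example shows. That is a reason to keep the present figure beside it, not to omit the at-risk one.

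**Conclusion.** The point holds conditionally. The difference in bases is plain from the text. The dilution is not certain: it needs at least one treated eye to be aphakic or pseudophakic at entry, which the documents allow but do not quantify, and it needs cataract events to arise in phakic eyes. Section 9.1.8 selects events by MedDRA coding, not lens status, so the second condition is an assumption. A reader might infer that the table must understate cataract risk; the documents do not support that, and the effect is zero if every treated eye is phakic. Under the two conditions the printed figure is the at-risk rate times the phakic share: half of it at 15 phakic eyes of 30, nine-tenths at 27.

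Nor should a surgery percentage above the cataract percentage be put down to the base alone. Under Protocol 11.3 a pre-existing condition is an AE only if it worsens, so an eye operated for a stable baseline cataract can count in 7.2.2 and not in 9.1.8.

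The effect is confined to one descriptive table. No event is lost, and neither the sample size nor the success criterion is touched. The change is worth making because cataract is an expected frequent harm and the correction is cheap.

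**What to change.** For the cataract rows of SAP 9.1.8 only:

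- Keep the percentage of all treated eyes, so that any cataract-coded event in a pseudophakic or aphakic eye stays visible.
- Add, by arm and for all treated eyes, the number and percentage with a cataract TEAE among treated eyes phakic at study entry, the base used in 7.2.2.
- At subject level, keep the present percentage and add the percentage among subjects with at least one treated eye phakic at entry, counting events in those eyes.
- Print both denominators in the table.

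Leave the elevated-IOP and complication rows as they are.

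The cost is a few lines of SAP text and extra rows in one table. No new data are needed, since lens status at entry is already used in 6.2, 7.2.2, 9.2.1 and 9.2.4. The downside is that the added rate may be higher and rests on fewer eyes: with 15 of 30 eyes phakic, 20% (95% CI 8-39%) is joined by 40% (16-68%). The change puts the event and the surgery on one base; it does not remove the other reason, given above, why surgery may exceed the event.
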